7.2.6 Drug-Induced Extrapyramidal Symptom Scale (DIEPSS)

The DIEPSS is a rating tool of extrapyramidal symptoms induced by antipsychotics and consists of 8 individual items; gait, bradykinesia, sialorrhea, muscle rigidity, tremor, akathisia, dystonia, and dyskinesia; and one global assessment; overall severity. The severity of each item is on a 5-point scale of 0 to 4. Dates of the assessments and the results will be recorded in the CRFs.

The DIEPSS total score (excluding overall severity) are the sum of the eight symptom scores.

7.2.7 Columbia-Suicide Severity Rating Scale (C-SSRS)

The C-SSRS is a rating tool designed to systematically assess and track suicidal behavior and suicidal ideation throughout the study. The C-SSRS can comprehensively identify suicidal events and limit the over-identification of suicidal behavior.

The Investigators will receive specific training before their initial assessment of C-SSRS. Date of the assessments and the results will be recorded in the CRFs.

7.2.8 Skin irritation assessment

The Investigator will evaluate any skin reactions at the application sites according to the Table 4 and record the score in the CRFs. If more than one skin reaction from + – to +++++ is observed at the application sites, the stronger reaction will be scored and recorded in the CRFs.

Table 4 Scoring of Skin Reactions

Skin condition		Score
No response	Negative	–
Erythema of the mild	Faint erythema	+ –
Erythema	Erythema	+
Erythema + edema	Erythema + Edema	++
Erythema + edema + papules, serous papules, vesicles	Erythema + Edema + Papules, Serous papules, Vesicles	++ +
Bulla major	Coalescing vesicles	++ + +

7.3 Other assessments

7.3.1 DAI-10

DAI-10's is an assessment for evaluating a drug adherence by adding the patient's attitude to the drug treatment compliance. Investigator will survey the subject's drug attitude ("true" or "false") for the following 10 items and record the assessment Date and the results to CRFs.

- 1) Good things about medication outweigh the bad
- 2) Feel like a zombie
- 3) Take of my own free choice
- 4) Feel more relaxed
- 5) Feel tired and sluggish
- 6) Take only when sick
- 7) Feel more normal
- 8) Unnatural for my mind and body to be controlled by medications
- 9) Thoughts are clearer
- 10) By staying on medication I can prevent a breakdown

7.3.2 EQ-5D

EQ-5D's is a self-administered, comprehensive rating scale developed to measure health-related quality of life. Investigator will use the questionnaire to investigate the following 5 items and record the assessment Date and the result to CRFs.

- 1) MOBILITY
 - 1: I have no problems in walking about,
 - 2: I have slight problems in walking about,
 - 3: I have moderate problems in walking about,
 - 4: I have severe problems in walking about,
 - 5: I am unable to walk about
- 2) SELF-CARE
 - 1: I have no problems washing or dressing myself,
 - 2: I have slight problems washing or dressing myself,
 - 3: I have moderate problems washing or dressing myself,
 - 4: I have severe problems washing or dressing myself,
 - 5: I am unable to wash or dress myself
- 3) USUAL ACTIVITIES (e.g. work, study, housework, family or leisure activities)
 - 1: I have no problems doing my usual activities,
 - 2: I have slight problems doing my usual activities,
 - 3: I have moderate problems doing my usual activities,

4: I have severe problems doing my usual activities,

5: I am unable to do my usual activities.

4) PAIN / DISCOMFORT

1: I have no pain or discomfort,

2: I have slight pain or discomfort,

3: I have moderate pain or discomfort,

4: I have severe pain or discomfort,

5: I have extreme pain or discomfort

5) ANXIETY / DEPRESSION

1: I am not anxious or depressed,

2: I am slightly anxious or depressed,

3: I am moderately anxious or depressed,

4: I am severely anxious or depressed,

5: I am extremely anxious or depressed

7.3.3 Questionnaire on dosage form

Investigator will ask Question 1 and Question 2 regarding the patch dosage form of antipsychotic, Question 3 regarding the DSP-5423P, and record the assessment Date and the results to CRFs.

- Would you like the patch dosage form to be available??

Response) "Yes" or "No"

- Is it easy for you to continue treatment with patches compared with tablets?

Response) "Yes," "Equal" or "No."

- Question 3 Would you like to use the patches that you used during this study in the future?

Response) "Yes" or "No"

7.4 Pharmacokinetic variable

7.4.1 Measurement

- Plasma concentration of bronanserin

- Plasma metabolite concentration

Cohort 1: M-1 (N-de-ethylated), M-2 (N-oxide), M-3 (7OH) (hydroxide), M-3 (8OH) (hydroxide), M-4 (ethylenediamine), and M-8 (carboxylic acid)

Cohort 2: M-1 (N-de-ethylated)

7.4.2 Survey variable

Investigator will record the following variable in CRFs. When subjects early terminate the study treatment, investigator will record the survey variables according to period at the time of termination [DSP-5423(tablet) or DSP-5423P].

DSP-5423 (tablet) treatment period:

Dates and times of blood sample collection, Dates and times of the last two administrations of DSP-5423 (tablet) before blood sample collection, DSP-5423 (tablet) doses of the last two administrations before blood sample collection, Yes or no for the question whether had a meal immediately before administrations of DSP-5423 (tablet) of the last two administrations before blood sample collection

DSP-5423P application period:

Dates and times of blood sample collection, Dates and times of the last two applications of DSP-5423P before blood sample collection, DSP-5423P doses of the last two applications before blood sample collection, Locations for the last two applications of DSP-5423P before blood sample collection

8. Statistical Analysis

8.1 General Considerations

For categorical variables, the number of subjects and percentage for each category will be calculated. Unless otherwise specified, all options in a category in CRFs should be presented regardless of whether they are actually selected. Missing (if no option in CRFs was selected) are presented as missing unless otherwise specified. The percentages are rounded to one decimal place. However, 0% is set to be a blank.

For continuous variables, summary statistic (n, Mean, SD, Min, Median, Max) will be calculated unless otherwise specified. Unless otherwise specified, mean and median should be rounded to one more decimal place of the observed value and SDs to two more of the observed value. If the summary statistic cannot be calculated (e.g., if the standard deviation is calculated with single data), period (.) should be presented. In summary of plasma drug concentration, the Geometric mean is rounded to one mode decimal place of observed value, and the CV% and Geometric CV% are rounded to one decimal place.

In summary of observed values and change, subjects with both baseline and each visit values are utilized for analysis.

All analyses will be conducted using SAS (Statistical Analysis System: SAS Institute, North Carolina, USA) version 9.4 or higher

8.2 Derived variables

When analysis is performed using derived variables, derived variables are handled without rounding, and the results are expressed with pre-specified digits. The derived variables in listing are presented based on pre-specified digits.

- BMI (kg/m²): Weight (kg) / (height (m) x height (m)). [one decimal point]
- Age at initial onset of schizophrenia (years): FLOOR ((onset date of initial episode – date of

birth)/365.25). [integer]

- Duration of illness (years): (date of informed consent – onset date of initial episode)/365.25. [integer]
- Duration of current episode (months): (date of informed consent – onset date of current episode)/(365.25/12). [integer]

The following item are calculated for DSP-5423 (tablet) treatment period and DSP-5423P treatment period, respectively.

- Duration of exposure (days): Last dose date –first dose date +1 [integer]
- The first dose date and last dose date: the initial administration date and the final administration date for each period. The final application date for patch and the date for completion of the patch are identical and those are the final application date for patch, not final removal date for patch.
- Treatment compliance (%): (total number of tablets/patches actually taken/applied x 100) / total number of tablets/patches that should have been taken/applied during each treatment period. [integer] If number of tablets/patches actually taken/applied is unknown, the treatment compliance is set to a missing.
- Mean daily dose (mg/day): Average of prescribed daily dose (mg). [integer]
- Maximum daily dose (mg/day): Maximum of prescribed daily dose (mg). [integer]
- Modal daily dose (mg/day): Most frequently of prescribed daily dose (mg/day). In the case that two or more dose are the most frequent dose, the maximum of them will be the modal daily dose.
- Last daily dose (mg/day): Prescribed daily dose of the last dose date (mg/day). [integer]
- Cumulative dose (mg): Sum of prescribed daily dose (mg/day) x duration of each prescription (days). [integer]

In calculation for number of tablets that should have been taken, if last date of prior description period and start date of following description period are same, prior description period are seen as up to day before of its last date. That is, the number of tablets prescribed and dose at last date of prior description period are seen as the number of tablets prescribed and dose in the subsequent period, and utilized for calculations.

- DAI-10 total score: sum of 1 (item 1,3,4,7,9, or 10 are true and item 2,5,6, or 8 are false) and –1 for other cases. [integer]
- Ratio of plasma metabolite concentration to plasma blonanserin concentration: plasma concentration of metabolite/plasma concentration of blonanserin [three decimal places]

8.3 Day 1

Day 1 is defined as the day of the initial application of DSP-5423P for each subject. Tab-Day1 is defined as the day of initial administration of DSP-5423(tablet) for subjects in Cohort 1.

8.4 Baseline

Baseline value for analysis (for the DSP-5423P treatment period) is defined as the last non-missing data on or prior to Day 1.

Regarding to Cohort 1, baseline value for the DSP-5423 (tablet) administration period (Tab-Baseline) is defined as the last non-missing data on or prior to the day of initial administration of DSP-5423(tablet).

8.5 Analysis Visit

Data of DSP-5423P treatment period is defined as the data captured on Day 1 through 7 days after the final application of DSP-5423P.

All data will be organized and analyzed according to the scheduled timing as outlined in Tables 1 and 2 Schedule of Assessments and according to the visit denoted in the CRFs. Unscheduled visits may not be used for any analysis unless otherwise specified. However, the data collected at the discontinuation visit within 7 days from the final application of study drug are mapped to the next scheduled visit of the actual discontinuation date. In listing, all data including unscheduled visit data should be presented.

1) CRF discontinuation visits in DSP-5423 (tablet) treatment period

Assessments and tests	Relative Day	Analysis Visit
PANSS, CGI-S, DIEPSS, body weight, body temperature, blood pressure, pulse rate	Tab-Day 1 to 11	Tab-W1, 2, 4, 6
	Tab-Day 12 to 18	Tab-W2, 4, 6
	Tab-Day 19 to 32	Tab-W4, 6
	Tab-Day 33 or later	Tab-W6
Laboratory test, ECG	Tab-Day 1 to 18	Tab-W2, 6
	Tab-Day 18 or later	Tab-W 6

The Tab-Day 1 is defined as the date of initial administration of DSP-5423 (tablet). CRF discontinuation visits in DSP-5423 (tablet) treatment period is defined as data on first non-missing (ex. no visit or results are missing) visit which meets all above requirements. Laboratory test and vital sign (body temperature, blood pressure, pulse rate) are performed visit handling for each item. Others are not considered as missing if they have any one component.

2) CRF discontinuation visits in DSP-5423P application period

Assessments and tests	Relative Day	Analysis Visit
PANSS, CGI-S, DIEPSS, C-SSRS,	Day 1 to 11	W1, 2, 4, 6, 8, 12, 16, 20, 24, 28, 36, 44, 52
	Day 12 to 18	W2, 4, 6, 8, 12, 16, 20, 24, 28, 36, 44, 52

Assessments and tests	Relative Day	Analysis Visit
Skin irritation assessment, body weight, body temperature, blood pressure, pulse rate	Day 19 to 32	W4, 6, 8, 12, 16, 20, 24, 28, 36, 44, 52
	Day 33 to 46	W6, 8, 12, 16, 20, 24, 28, 36, 44, 52
	Day 47 to 60	W8, 12, 16, 20, 24, 28, 36, 44, 52
	Day 61 to 92	W12, 16, 20, 24, 28, 36, 44, 52
	Day 93 to 120	W16, 20, 24, 28, 36, 44, 52
	Day 121 to 148	W20, 24, 28, 36, 44, 52
	Day 149 to 176	W24, 28, 36, 44, 52
	Day 177 to 204	W28, 36, 44, 52
	Day 205 to 267	W36, 44, 52
	Day 268 to 323	W44, 52
	Day 324 or later	W52
Laboratory test, ECG	Day 1 to 18	W2, 6, 12, 20, 28, 36, 44, 52
	Day 19 to 46	W6, 12, 20, 28, 36, 44, 52
	Day 47 to 92	W12, 20, 28, 36, 44, 52
	Day 93 to 148	W20, 28, 36, 44, 52
	Day 149 to 204	W28, 36, 44, 52
	Day 205 to 267	W36, 44, 52
	Day 268 to 323	W44, 52
	Day 324 or later	W52
DAI-10, EQ-5D, Plasma drug concentration	Day 1 to 46	W2, 6, 12, 20, 28, 36, 44, 52
	Day 47 to 204	W28, 36, 44, 52
	Day 205 or later	W52

Day 1 is defined as the day of the initial application of DSP-5423P for each subject. CRF discontinuation visits in DSP-5423P treatment period is defined as data on first non-missing (ex. no visit or results are missing) visit which meets all above requirements. Laboratory test and vital sign (body temperature, blood pressure, pulse rate) are performed visit handling for each item. Others are not considered as missing if they have any one component.

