Body temperature, blood pressure, pulse rate		X	X ^{d)}	X	X	X	X ^{e)}	X	X	X	X	X	X	X	X	X	X	X	X	X	X	X	
Adverse event monitoring			←																			→	
Blood sampling for PK					X		X ^{e)}			X							X			X	X		
Questionnaire																				X	X		

- a) Tab-Day 1 is defined as the day of the initial administration of DSP-5423 (tablet), and Day 1 is defined as the day of the initial application of DSP-5423P.
- b) At Visit 2 (before administration initiation of DSP-5423 (tablet)), Visit 6 (the end of DSP-5423 (tablet) treatment phase) and Visit 113 (the end of DSP-5423P treatment phase), blood samples will be collected under fasting conditions (at least 10 hours after the last meal). At other visits, blood samples should be collected under fasting conditions (at least 10 hours after the last meal) whenever possible.
- c) To be performed only in female subjects who are premenopausal and of childbearing potential.
- d) Must be performed before the beginning of treatment with DSP-5423 (tablet). For the subject treated with any antipsychotic, must be performed after discontinuation of antipsychotics and before the beginning of treatment with DSP-5423 (tablet).
- e) Must be performed before the beginning of treatment with DSP-5423P.
- f) If the subject discontinues the study drug during the DSP-5423 (tablet) treatment phase, the subject will undergo the following safety assessments: study treatment compliance, DIEPSS, C-SSRS, laboratory test, pregnancy test, 12-lead ECG, body weight, body temperature, blood pressure, pulse rate, and adverse event monitoring at the discontinuation visit.
- g) Must be performed before the initiation of post-treatment with antipsychotics excluding the study drug.

Table 3 Schedule of Assessments (Cohort 2)

		DSP-5423P treatment phase (52 weeks)															Discontinuation	Follow-up phase (1-2 weeks)	
Visit No.	-	1	2	101	102	103	104	105	106	107	108	109	110	111	112	113			
Timeline from initiation of DSP-5423P application	-	Screening	Baseline	Week 1	Week 2	Week 4	Week 6	Week 8	Week 12	Week 16	Week 20	Week 24	Week 28	Week 36	Week 44	Week 52			
Visit window (Day)		-28-	-2-1	5-11	12-18	26-32	40-46	54-60	78-92	106-120	134-148	162-176	190-204	239-267	295-323	351-379	At discontinuation +5	6~17 days after completion of treatment or discontinuation	
Obtaining informed consent	X																		
Patient demographics and medical history	X																		
Dispense study drug		X ^{a)}	X	X	X	X	X	X	X	X	X	X	X	X	X				

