15.3.6.5 C-SSRS

The number and percentage of subjects with either suicidal ideation or suicidal behavior at least once in DSP-5423P application period will be summarized.

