8.6 LOCF endpoint

The last observation from Day 1 through 7 days after the final application of DSP-5423P, except for baseline data defined in section 8.4, will be carried forward and will be defined as the Week 52 (LOCF).

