9.12.6 C-SSRS

C-SSRS will be summarized for each cohort and cohort total, and baseline for Cohort 1 is defined as baseline at DSP-5423(tablet) treatment period and one for Cohort 2 is defined as baseline at DSP-5423P application period.

For ‘Suicidal ideation’, the number and percentage of subjects by items, with any suicidal ideation, with no suicidal ideation, with serious suicidal ideation defined as ‘Yes’ in item 4 or item 5, will be summarized at baseline, each visit, entire DSP-5423(tablet) treatment period, and entire DSP-5423P application period.

Suicidal ideation

1. Wish to be dead
2. Non-specific active suicidal thoughts
3. Active suicidal ideation with any methods [not plan] without intent to act
4. Active suicidal ideation with some intent to act, without specific plan
5. Active suicidal ideation with specific plan and intent

For ‘Suicidal behavior’, the number and percentage of subjects by items, with any suicidal behavior, and with no suicidal behavior will be summarized at baseline, each visit, entire DSP-5423(tablet) treatment period, and entire DSP-5423P application period.

Suicidal behavior

1. Any actual attempts

2. Any interrupted attempts
3. Any aborted attempts
4. Any preparatory acts or behavior

The number and percentage of subjects with either suicidal ideation or suicidal behavior as ‘any suicidality’, and with no suicidality will be summarized at baseline, each visit, entire DSP-5423(tablet) treatment period, and entire DSP-5423P application period.

The subjects* with ‘emergence of suicidal ideation’ defined as subjects without suicidal ideation at baseline, but not in post-baseline of DSP-5423P application period, subjects* with ‘serious emergence of suicidal ideation’ defined as subjects with ‘No’ in both item 4 and item 5**, but not in post-baseline of DSP-5423P application period, subjects* with ‘emergence of suicidal behavior’ defined as subjects with no suicidal behavior at baseline, but not in post-baseline of DSP-5423P application period, subjects* with “emergence of suicidality” defined as subjects with neither suicidal ideation nor suicidal behavior, but either/both in post-baseline of DSP-5423P application period, subjects with ‘any completed suicide’, will be summarized based on the number and percentages.

* Subject with ‘Yes’ at baseline are not included in the denominator of percentages.

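### SAP 8.5 omits the baseline exclusion found in 8.6, so a pre-patch C-SSRS rating dated Day 1 can be counted as patch-period data

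*SAP*

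**What the plan says.** **Window.** SAP 8.5 states: "Data of DSP-5423P treatment period is defined as the data captured on Day 1 through 7 days after the final application of DSP-5423P". SAP 8.3 makes Day 1 a calendar day: "Day 1 is defined as the day of the initial application of DSP-5423P for each subject". Neither section refers to clock time.

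**Baseline.** Under SAP 8.4 the patch-period baseline "is defined as the last non-missing data on or prior to Day 1". Baseline may therefore also fall on Day 1.

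**LOCF.** SAP 8.6 uses the same span, Day 1 to 7 days after the last application, but adds "except for baseline data defined in section 8.4". The protocol's LOCF definition (15.3.10.4) has no such exclusion, so it was added in the SAP, and only there.

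**Visit rule.** SAP 8.5 also says data are organized by the schedule tables and the CRF visit. The Cohort 1 schedule puts Visit 6 under the tablet phase and labels it both as tablet Week 6 and as baseline.

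**Timing of the pre-patch C-SSRS.** For Cohort 1 Visit 6, footnote e of Protocol Table 2 reads "Must be performed before the beginning of treatment with DSP-5423P"; the window is Tab-Day 40 to 43. Cohort 2 Visit 2 carries the same requirement (Protocol Table 3, footnote d), with window Day -2 to 1.

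**C-SSRS summaries.** Protocol 15.3.6.5 counts subjects with "either suicidal ideation or suicidal behavior at least once in DSP-5423P application period". SAP 9.12.6 reports ideation, behavior and any suicidality at baseline, at each visit and over each whole treatment period. It sets the reference differently by cohort: "baseline for Cohort 1 is defined as baseline at DSP-5423(tablet) treatment period", while Cohort 2 uses the patch baseline.

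**The concern.** A rating that must be completed before any patch is applied describes the patient's state before patch exposure. If it is dated Day 1, the window in 8.5 nevertheless treats it as patch-period data. Same-day rating is within the design. The Cohort 2 window includes Day 1. In Cohort 1, six weeks of tablets end on Tab-Day 42, so a Visit 6 on Tab-Day 43 can be the day of the first patch.

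Other safety summaries guard against this by limiting themselves to post-baseline data: markedly abnormal laboratory values (SAP 9.12.2), weight (9.12.3), the ECG listings (9.12.4) and the maximum skin score (9.12.7). The whole-period C-SSRS counts carry no such limit.

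Safety of the patch is the primary objective, safety of switching is a secondary one, and the C-SSRS is a named safety endpoint. The study is uncontrolled, so there is no concurrent arm in which the same miscount would occur and offset it.

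**Working it through.** The documents give no figure for this point, so there is nothing to reproduce. The check applies the SAP rules to each permitted date, then scales the possible effect under stated assumptions.

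**Step 1: classify a pre-patch rating by its date** (taking it to be the last non-missing value before the patch).

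| Date of rating | In 8.5 patch period | Baseline under 8.4 | In LOCF under 8.6 |
|---|---|---|---|
| Day -2 or -1 | No | Yes | No |
| Day 1 | Yes | Yes | No |

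Only the Day 1 rating is both baseline and patch-period data.

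**Step 2: follow the Day 1 rating into SAP 9.12.6.**

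- *Whole-period counts, both cohorts.* No post-baseline limit applies, so under the literal 8.5 window the rating is included.
- *Emergence, Cohort 2.* The C-SSRS baseline is the patch baseline. A subject positive on that rating is baseline-positive and leaves the denominator; a negative rating adds nothing. This count is protected.
- *Emergence, Cohort 1.* The C-SSRS baseline is the pre-tablet rating. A subject negative then and positive at a Day 1 Visit 6 has a positive rating that is later than the C-SSRS baseline and inside the 8.5 window. It can be read as emergence in the patch period.
- *Tablet period, Cohort 1.* Nothing in 8.5 removes Visit 6 from the tablet period. The same rating could count in both periods; the tablet count does not fall.

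**Step 3: scale.** Let f be the share of pre-patch ratings dated Day 1, p0 the proportion positive at that rating, and r the proportion of those subjects who are positive again later on the patch and so would be counted anyway.

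Excess subjects per 100 = 100 × f × p0 × (1 − r)

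None of f, p0 or r is in the documents; all values below are assumptions.

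- f = 0: excess 0, whatever p0 and r.
- f = 0.5, p0 = 5%, r = 60%: 100 × 0.5 × 0.05 × 0.4 = 1.0.
- f = 1, p0 = 10%, r = 30%: 100 × 1 × 0.10 × 0.7 = 7.0.

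If later ideation were independent of the pre-patch rating, r would equal the true on-patch rate. With a true rate of 5% and p0 = 10%, the excess is 100 × 0.5 × 0.10 × 0.95 = 4.75 at f = 0.5 and 9.5 at f = 1, against a true count of 5.0 per 100. With p0 = 20% and f = 1 it is 100 × 1 × 0.20 × 0.95 = 19.0. That is an outer bound on stacked assumptions, not an estimate.

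**Step 4: after the fix.** With baseline data excluded from the 8.5 window and only post-application ratings used in 9.12.6, the excess is 0 for every f, p0 and r.

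**The case against.** The strongest reply is that SAP 8.5 also organizes data by CRF visit. The schedule puts Visit 6 in the tablet phase, Protocol section 10 describes it as a visit of the tablet period, and Protocol 11.3.5 treats it as the end of tablet administration. SAP 9.12.6 also lists baseline separately from the whole patch period. A programmer working by visit would keep Visit 6 out of the patch counts. This stands as a plausible reading, and for that reason miscounting is possible, not certain. It does not remove the point: 8.5 gives two rules and no precedence, and Cohort 2 Visit 2 has no tablet phase to be assigned to.

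On emergence, the SAP speaks of post-baseline within the patch period, and 8.4 defines a baseline for that period. On that reading Visit 6 is the patch baseline and drops out. This is reasonable too, but 9.12.6 sets its own Cohort 1 baseline and does not say which one governs the term.

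A reader might infer more than the text supports:

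- *That pre-patch ideation in general is counted in the patch period.* Ratings on Day -2 or -1 fall outside even the literal window.
- *That the rating usually falls on Day 1.* The windows permit it; neither document gives the share.
- *That suicidality is moved from tablet to patch.* Nothing is taken out of the tablet period, so the worst case is double counting.
- *That some minimum number of subjects must be affected.* Any such floor comes from the assumed inputs. Exclusion criterion 7 addresses active suicidal ideation and Protocol 13.1 lists suicide ideation as a reason for termination; both could lower the pre-patch rate.

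The C-SSRS summaries are descriptive, also given by visit, and listed by subject. A contribution from Visit 6 could therefore be traced, but the summary count would still be ambiguous.

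The same-day convention for adverse events in SAP 9.12.1 does not settle the matter, because it is stated for adverse events only.

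**Conclusion.** The point holds in a limited form. SAP 8.5, read literally, admits a pre-patch C-SSRS rating dated Day 1 to the patch period and conflicts with the visit rule in the same section. The whole-period ideation, behavior and any-suicidality counts are exposed in both cohorts. Emergence is exposed in Cohort 1 only, and only on one of two reasonable readings.

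The size is unknown. It is zero if no pre-patch rating is dated Day 1 or none of those is positive. With 5–10% positive before the patch, 30–60% of those positive again later, and anywhere from none to all rated on Day 1, the excess runs from 0 to 7 per 100. This should be corrected because it bears on a named safety endpoint and costs little to resolve. It does not call the design into question.

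**What to change.** 1. In SAP 8.5, add to the definition of patch-period data the exclusion already used in 8.6: "except for baseline data defined in section 8.4".
2. In SAP 9.12.6, state that patch-period and emergence counts use only C-SSRS ratings made after the first application, and that the pre-patch Visit 6 rating belongs to the tablet period. The first change alone is not enough in Cohort 1, because 9.12.6 sets a C-SSRS baseline there that differs from the patch baseline in 8.4.

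Protocol 11.3.3 has only the date of the C-SSRS recorded, so order within Day 1 should be taken from the CRF visit: Visit 6 and Visit 2 are required to precede the patch. Any such rating known to have been made after application should be handled as a documented deviation.

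The cost is two sentences in the SAP and the matching filter in Tables 14.3.8.1 to 14.3.8.4. No new data are needed.
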